6. STUDY TREATMENT AND REGIMEN

Flow Diagram 1: Patient pathway

Page 32 of 53

FISS Protocol Final Version 1.0 date 24-Jul-2025

6.1 IDENTIFICATION AND SCREENING

Participants will be identified from 10 stroke services across the UK. Patients who are aged 18 or over who have a confirmed stroke diagnosis (CT or MRI scan) and are deemed as potentially eligible will be approached about the FISS study.

The initial approach will be from a member of staff from the participating stroke service (which may include the PI, research team, hospital or community service). Flexible study recruitment will reflect local clinical practice and will allow participants to be approached by a member of the recruiting service as an in-patient (e.g. the stroke unit or other department within the recruiting trust such as A&E or a rehabilitation unit), an out-patient at a follow-up appointment or once they have been discharged home. The initial approach could be done in person, by letter/email (discharge pack) or by phone. Information about the study may also be on display in the relevant clinical areas (at each individual stroke service's discretion).

The PI (or delegate) will inform the participant or their personal consultee, of all aspects involved in the participation in the study. Sufficient time will be given for the patient to consider participation, and the patient will be given the opportunity to ask questions throughout the process. Consent will be taken from patients directly in hospital or remotely via electronic consent, or where patients lack capacity to complete consent, advice may be given by a personal consultee. No study specific assessments will be undertaken prior to informed consent provided.

It will be explained to the potential participant that entry into the study is entirely voluntary and that their treatment and care will not be affected by their decision to participate. It will also be explained to patients prior to joining the study, that they can withdraw at any time but that attempts may be made to avoid this occurrence. In the event of their withdrawal of consent from all study activities, it will be explained that their data collected so far cannot be erased and we will use the data in the final analyses where appropriate. This information will be reiterated at the point of receiving the withdrawal request.

If needed, the usual local NHS interpreter and translator services will be available to assist with discussion of the study, the PIS, and consent forms.

6.1.1 Baseline

Following consent but prior to randomisation, baseline data will be collected, this will include (but not limited to) demographic and contact details and the following baseline questionnaires:

- Nottingham Extended Activities of Daily Living (NEADL) [14]
- Short Falls Efficacy Scale-International (Short FES-I) [13]
- Patient Health Questionnaire 8 (Participant PHQ-8) [15]
- Modified Barthel Index (MBI)
- Quality of Life (EQ-5D-5L) [16]
- Health Resource Questionnaire
- Patient Health Questionnaire 8 (Carer PHQ-8)*

Baseline data will be collected by research staff or FISS trained stroke healthcare professionals once they are discharged, either in person at the participant's home or over the phone, where possible. Data will be captured directly into REDCap, or where an electronic device is not available, into a paper workbook transcribed into REDCap.

Participants will be randomised using a web-based, concealed randomisation system to receive either the SAF intervention in addition to usual care or usual care alone. The participant

Page 33 of 53

FISS Protocol Final Version 1.0 date 24-Jul-2025

will be told by a member of stroke service which arm of the study they have been randomised to at the time of randomisation (where possible) or as soon after randomisation is completed.

Baseline data collection and randomisation is likely to take place on the same day and will need to be collected within 28 days of discharge as per remote consent. Where this is not possible, randomisation can take place remotely and the participant contacted to inform them of their treatment allocation. This will need to be within 1 or 2 days of collecting the baseline data.

*The Carer PHQ will be posted to the participant's contact address once the participant is randomised. The baseline carer PHQ will be completed by the carer (electronic or post) and returned to the NCTU. Where randomisation is done in person and the carer is available, this can be done at the point of randomisation.

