4. DETAILS OF INTERVENTION

4.1 DESCRIPTION

The SAF Intervention is an expert-led, manualised self-management approach to reduce falls, using a training package, education booklet and a checklist and action plan that is individualised for each stroke patient (participants). The healthcare professional training will include all the information a healthcare professional requires to deliver the SAF intervention to stroke patients, with associated communication support documentation. The SAF checklist includes a definition of a fall along with a list of risk factors and suggested actions on several key themes including falls history, medical history and environment. The action plan is where the stroke patient's individual risks and actions are recorded to be used as a reminder of the actions they need to take and provide a place for them to track their own progress of complete and outstanding actions.

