4.4 FISS FALLS DIARY

All study participants will be given a Falls Diary, for their personal use, which will be posted to them by the central research team following randomisation. The Falls Diary will contain a definition of a fall. Participants will be asked to record the number of falls they have over each month and record the severity of the fall based on fall outcome in line with the NDNQI definitions (e.g. fall resulted in injury that required surgery would be classed as 'major' or for FISS participant documentation, category D). Participants will be encouraged to use the Falls Diary, but use of the diary is not a requirement of the study. Falls Diaries will not be collected or used as source data.

Reminders (electronic or telephone) to participants to report monthly falls data will be coordinated by the central research team. Participants will have the option to provide falls data by post, online form or telephone. Reminders and follow-up calls may be made for non-responders. Participants will be followed up a maximum of twice each month to ask for falls data.

To ensure accurate data collection, the database will be restricted to allow falls data entry only within a one-year period from the randomisation date. Any falls occurring before or after this period will be prevented from being recorded in the system.

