7.2.3 Assessment of efficacy

Primary outcome: The evaluation of the primary outcome will be performed using a negative binomial model that includes the minimisation factors (stroke service, living alone or with others, aged >65 years or <=65 years and baseline modified Barthel Index (MBI) score of >14 or <=14). The model will incorporate exposure time to estimate the between group difference which will be summarised using the incident rate ratio (IRR) and its associated 95% confidence interval.

The primary analysis will be 'as randomised' with no imputation of missing data.

Sensitivity analyses: Sensitivity analyses will be conducted to investigate the impact of missing data using techniques such as multiple imputation and may also include alternative models where visual inspection of the baseline variables show marked imbalances in potentially prognostic variables, between groups. Further sensitivity analyses may be performed if participants show major non-compliances (e.g., who do not receive the intervention when randomised to do so or receive the intervention when randomised to standard care alone).

Sub-group analyses: Exploratory subgroup analyses for the primary outcome will be performed according to the minimisation variables by including appropriate interaction terms

Page 39 of 53

FISS Protocol Final Version 1.0 date 24-Jul-2025

in the primary model. The interpretation of any subgroup effect will be based on the interaction tests (i.e., evidence of differential treatment effects in different subgroups). It is acknowledged that these investigations will not be adequately powered.

Secondary outcomes: Secondary outcomes will be analysed using appropriate regression models which include the minimisation factors and the baseline value of that variable where available. Continuous outcomes will be analysed using linear mixed models and count/rate outcomes will be analysed using negative binomial models. Associated measures of the between treatment difference, such as the difference in means or incidence rate ratio, will be presented alongside 95% confidence intervals. The secondary analyses will be considered supportive to the primary and interpreted in that light, and no multiplicity adjustments will be made.

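### Falls before randomisation are neither a named baseline item nor a covariate in the primary model, which gives up some precision and a balance check

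*Protocol*

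**What the plan says.** **Baseline data.** Protocol section 6.1.1 states that "baseline data will be collected, this will include (but not limited to) demographic and contact details and the following baseline questionnaires". It then names NEADL, Short FES-I, PHQ-8, the Modified Barthel Index, EQ-5D-5L, a health resource questionnaire and the carer PHQ-8. Short FES-I measures fear of falling, not falls. Table 6 (section 6.2) starts fall recording at month 1 and has no falls entry at baseline.

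**Falls entry in the database.** Section 4.4 says that "the database will be restricted to allow falls data entry only within a one-year period from the randomisation date", and adds: "Any falls occurring before or after this period will be prevented from being recorded in the system".

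**Primary model.** Section 7.2.3 specifies a "negative binomial model that includes the minimisation factors" (stroke service, residence, age group and Barthel group), with exposure time. Section 7.2.1 says the same. Further covariates appear only among the sensitivity analyses, which "may also include alternative models where visual inspection of the baseline variables show marked imbalances in potentially prognostic variables".

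**Secondary outcomes.** These, including the falls counts, are adjusted for their own baseline value if there is one (section 7.2.3).

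**The SAF checklist.** Section 4.1 describes "a list of risk factors and suggested actions on several key themes including falls history, medical history and environment". Section 4.3 has it given to intervention participants at Session 1, up to two weeks after randomisation.

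**The concern.** The trial's outcome is falls, and its own intervention treats falls history as a risk-factor theme. Yet no named baseline item records falls before randomisation, and the specified primary model has no term for them.

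Two things are at stake:

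- **Precision.** Most of the variance behind the sample size is variation between people in their fall rate. A person-level predictor of that rate can reduce it.
- **Balance.** Minimisation does not act on prior falls. The imbalance-triggered sensitivity analyses can respond only to variables that were recorded, so an unrecorded imbalance in prior fallers would go unseen.

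Timing matters too. A statistical analysis plan finalised before database lock can add a model term, but it cannot recover a pre-randomisation measurement that was never taken. Baseline collection is therefore a matter for the protocol.

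**Working it through.** **Inputs (section 7.2.2).** Control rate 2.5 and intervention rate 1.675 falls per year (rate ratio 0.67), dispersion k = 1.1, two-sided 5% level, 90% power, 10% loss of primary outcome data. Follow-up is one year and allocation is 1:1.

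**Step 1: reproduce the plan's figure.** For the log rate ratio, per arm:

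n = (1.960 × √V0 + 1.282 × √V1)² / (ln 0.67)²

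- V1 = 1/2.5 + 1/1.675 + 2 × 1.1 = 0.400 + 0.597 + 2.200 = 3.197.
- V0, with the average rate of 2.0875 under the null: 2 × (1/2.0875 + 1.1) = 3.158.
- (ln 0.67)² = 0.1604.
- n = 207.9, so 208 per arm and 416 evaluable, as stated.
- 208/0.9 = 231.1, so 232 per arm and 464 randomised, as stated.

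Setting V0 = V1 (true rates) gives 209.5 per arm, or 420 in total, which is within 1% of 416. No covariate enters this calculation, so leaving out prior falls does not make it wrong.

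**Step 2: what a covariate could act on.** Of the 3.197 variance units, 2.2 (2.2/3.197 = 69%) come from dispersion.

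**Step 3: size of the gain.** The documents give no figure for what prior falls explain. The assumption is a cut of 5 to 30% in k, beyond what the minimisation factors already explain. With V0 = V1 = 0.997 + 2k:

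| Assumed cut in k | k | V1 | Evaluable N for 90% power | Power at 208 per arm |
|---|---|---|---|---|
| 0% | 1.100 | 3.197 | 420 | 89.8% |
| 5% | 1.045 | 3.087 | 406 | 90.8% |
| 10% | 0.990 | 2.977 | 392 | 91.7% |
| 20% | 0.880 | 2.757 | 362 | 93.6% |
| 30% | 0.770 | 2.537 | 334 | 95.2% |

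On the log scale the confidence interval narrows by 1 − √(3.087/3.197) = 1.7% at the low end and by 1 − √(2.537/3.197) = 10.9% at the high end.

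**Step 4: could another source fill the gap?** The SAF checklist is a one-arm, post-randomisation document. Monthly falls reports begin one month after randomisation. Neither can give a baseline value common to both arms.

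**The case against.** **The baseline list is open.** It says in terms that it is not exhaustive, and the case report form is not shown. A reader might infer that prior falls are certainly not collected, or are recorded only in the SAF arm. The documents do not establish either. What stands is that nothing commits services to collecting them, so the first step is to confirm.

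**The database restriction.** A reader might take section 4.4 to forbid a falls-history item. It sits with the falls diary and monthly reports and appears to govern outcome entry. Read literally it covers any earlier fall, so a clarifying sentence is worthwhile, but it is not proof of a bar.

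**The model is not closed.** The protocol says that the model includes the minimisation factors, not that it contains nothing else, and the analysis plan could add a term. That helps only if the variable has been recorded.

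**Nothing is wrong or contradictory.** This is correct. Adjusting for the minimisation factors fits the design. Baseline adjustment of secondary outcomes is conditional on a value existing, so it does not conflict with the primary model.

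**The gain is assumed.** This also stands. Age, Barthel group, residence and service already explain part of the variation, and only the increment beyond them counts. The value 1.1 is an upper confidence limit from a care-home study, and the protocol does not say whether it came from an adjusted model. Section 4.1 does not say which period its falls history covers, or how strongly it predicts falls after stroke.

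**Measurement.** Recall will be imperfect and sometimes by proxy. A raw count since the stroke would cover unequal periods, because inpatient stays differ and baseline data may be collected up to 28 days after discharge.

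**Conclusion.** The point holds as a cheap improvement. Prior falls are not among the named baseline items or in the specified primary model, and the SAF checklist cannot supply them for both arms. The loss is some precision in the primary estimate and a check of balance on prior falls.

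A reader might infer that the primary comparison is biased or the trial underpowered. The documents support neither. Randomisation protects the comparison without this covariate, and the stated sample size and power reproduce from the protocol's own inputs.

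If prior falls removed 5 to 30% of the dispersion of 1.1 beyond the minimisation factors, power at 208 per arm would rise from about 90% to about 91 to 95%. That range is an assumption. The low end, about one percentage point, is plausible because the existing factors may already capture part of the effect.

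**What to change.** 1. **Section 6.1.1 and Table 6:** confirm that the baseline form records falls before randomisation in both arms. If it does not, add a falls-history item over one defined recall period, with proxy report allowed.
2. **Section 4.4:** state that the one-year restriction applies to entry of outcome falls and does not block this baseline item.
3. **Section 7.2.3:** prespecify the item as a covariate in the primary negative binomial model, in a simple form such as none, one, or two or more. If the period differs between people, use a rate instead. State the rule for missing values, for instance a separate missing category.

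**Cost.** One or two recall questions in an existing baseline interview and one model term, with some recall error and some missing values. Anyone randomised before the item is added gains nothing from it, because a true pre-randomisation report cannot be obtained later; the missing-value rule must cover them.

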Data Management	Not blinded	Data management staff will have access to the unblinded datasets within the study database to ensure data quality and undertake central monitoring activities. They will have access to all data fields across the SAF intervention participants and usual care.
Study Statistician and Senior Study Statistician	Blinded	The study and senior study statistician will not have access to intervention allocations or data which has the potential to unblind until after the first database lock for the analysis.
Independent Statistician	Not blinded	A statistician, independent to the study team, will be responsible for the generation of closed reports for the Data Monitoring Committee (DMC) and other reports with potentially unblinding data and will therefore be unblinded to study treatment allocations.

Maintenance of randomisation codes and procedures for breaking code

The stroke service staff, Falls Leads and participants (and carers and/or friends/relatives as applicable) will be aware of which arm the participant is randomised to. Therefore, there is no process required for code breaking. NCTU will retain the randomisation codes for participants for the duration of the study.

At their request, the DMC may review unblinded data. This will be prepared by a statistician from NCTU not involved in the study (i.e., an independent statistician), who will store all unblinded output in a secure and access-controlled area.

The study statistician will receive the treatment allocation only after the SAP has been finalised and approved, and the database has been locked.

Page 24 of 53

FISS Protocol Final Version 1.0 date 24-Jul-2025

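### The baseline carer PHQ-8 can be completed after allocation is known, yet it serves as the baseline covariate, so the adjusted carer effect may be biased

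*Protocol*

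**What the plan says.** Protocol section 6.1.1 opens with the rule "Following consent but prior to randomisation, baseline data will be collected", and the list that follows includes the Carer PHQ-8, marked with an asterisk. The footnote to that asterisk sets a different timing. The form goes by post to the participant's "contact address once the participant is randomised. The baseline carer PHQ will be completed by the carer", who returns it to the trials unit electronically or by post. It gives no deadline. It allows one other route: "Where randomisation is done in person and the carer is available, this can be done at the point of randomisation".

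The same section says the participant is told the arm "at the time of randomisation (where possible) or as soon after randomisation is completed". Section 5.2.2 adds that "participants (and carers and/or friends/relatives as applicable) will be aware of which arm the participant is randomised to". Section 4.3 places SAF session 1 in the first two weeks after randomisation and allows a family member or carer to take part.

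Table 6 shows the carer PHQ at month 0, month 6 and month 12, and Table 3 makes the 6- and 12-month values a secondary endpoint. Sections 7.2.1 and 7.2.3 put the minimisation factors and "the baseline value of that variable where available" into each secondary-outcome model. Nothing exempts the carer PHQ from this rule or limits the covariate to forms completed before randomisation.

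**The concern.** Adjusting for a baseline value is safe because randomisation makes its expected difference between arms zero. That guarantee is lost once the value can be recorded after allocation is known. A carer who learns that the participant will receive SAF, or who sits in on session 1, may score differently from a carer who learns that nothing will be added to usual care. The covariate then carries part of the response to allocation, and the model subtracts it from the treatment effect.

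There is a second route to bias. Whether the form comes back at all may depend on the arm. If carers without a baseline value drop out of the model, those who remain may no longer be a randomised comparison.

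At stake is the estimate for one stated secondary objective, carer psychological stress. The loss cannot be repaired later: an analysis plan can drop the covariate, but it cannot recover a pre-randomisation score that was never collected.

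**Working it through.** **The plan's own figures.** The protocol gives no effect size, standard deviation, correlation or return times for the carer PHQ, so there is no carer figure to reproduce. Its only power calculation is for falls (section 7.2.2), and it reproduces. With rates of 2.5 and 1.675, dispersion 1.1, 90% power and two-sided 5%, n per arm = (1.960 + 1.282)² × (1/2.5 + 1/1.675 + 2 × 1.1) / ln(0.67)² = 209.5, or 207.9 with the null variance taken at the average rate, against the stated 208. Then 208 / 0.9 = 231.1, which rounds up to 232 per arm and 464 in total. None of this involves the carer PHQ.

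**Sequence of events for the carer form.**
1. Day 0: randomisation, with the arm disclosed then or soon after (6.1.1).
2. Day 0 or later: the form is posted, or is completed on the spot if the carer is present (6.1.1 footnote). The order relative to disclosure is not fixed.
3. Up to week 2: SAF session 1, possibly with the carer (4.3).
4. No deadline is set for the baseline form. Section 6.2.3 allows about four weeks for follow-up questionnaires. If that also applies here, which is an assumption, forms could be completed after session 1 and around session 2.

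**Effect on the estimate.** In a baseline-adjusted linear model:

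adjusted effect = (arm difference at follow-up) − b × (arm difference in the covariate)

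where b is the within-arm slope of follow-up on the covariate. Let f be the share of the follow-up effect already present when the form is completed. If the true effect is D, the covariate difference is f × D, so

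adjusted effect = D − b × f × D = D × (1 − b × f).

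Both b and f are assumptions. Share of the effect retained:

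| f | b = 0.3 | b = 0.5 | b = 0.7 |
|---|---|---|---|
| 0 | 100% | 100% | 100% |
| 0.10 | 97% | 95% | 93% |
| 0.25 | 92.5% | 87.5% | 82.5% |
| 0.50 | 85% | 75% | 65% |

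Simulation at f = 0, 0.25 and 0.50 agrees to within about one percentage point (for example 88.1% at f = 0.25, b = 0.5, and 65.2% at f = 0.50, b = 0.7).

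If the early shift runs against the later effect, f is negative and the estimate is inflated. At f = −0.25 the factor is 1 + 0.25b, or 107.5%, 112.5% and 117.5% for the three slopes.

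**With a true baseline.** If every form used is completed before allocation, the expected covariate difference is zero and the factor is 1 whatever the slope.

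**The case against.** The strongest case on the other side has four parts.

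- **Scope.** This is one outcome. The synopsis marks the carer measure as optional, and section 7.2.3 calls secondary analyses supportive. That stands, and it limits the severity.
- **The in-person route.** Baseline collection and randomisation are expected on the same day, and a carer who is present can complete the form then. Such forms may carry little or no shift. This reduces the problem but does not remove it: it depends on the carer being there, and the form need not come before disclosure. The protocol does not say what proportion will use each route.
- **Early change may be negligible.** A reader might infer that adjustment must remove part of any SAF effect on carers. The protocol does not support that. Bias needs an early shift in scores, its direction depends on the direction of that shift, and no carer data are given from which to judge either. The larger losses in the table show what the formula gives; they are not a forecast.
- **The analysis plan could settle it.** Which dated forms count as baseline is ordinary content for a SAP, which is not shown here. This stands for the covariate rule, but not for the timing of collection, which is fixed in the protocol and contradicts itself within section 6.1.1.

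**Conclusion.** The point holds in a conditional form. The protocol contradicts itself on when the carer PHQ-8 is collected. By default it is collected after randomisation by someone who knows the arm, and the general rule for secondary outcomes then uses it as a covariate. The adjusted carer effect may be biased in either direction, or not at all if scores have not moved. Under the assumed ranges, 93-97% of the effect is retained at f = 0.10 and 65-85% at f = 0.50, for slopes of 0.7 to 0.3. Return of the form may also differ by arm.

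Severity is moderate. A reader might take this as a threat to the trial's main conclusion. It is not: the falls outcome, the sample size and the participant-reported outcomes are untouched.

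**What to change.** 1. Reconcile the footnote with the opening of section 6.1.1. Offer the carer PHQ-8 at the baseline contact, in person, by phone or by link, for completion before allocation is generated where possible, without delaying randomisation.
2. Record the completion date, and for same-day forms whether completion came before randomisation.
3. Add a sentence to section 7.2.3: only forms completed before randomisation serve as the baseline covariate, and later forms count as missing baseline. Whether a carer has a usable value is then settled before allocation, so it cannot depend on the arm.

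The cost is one short form moved earlier and one added sentence. Some carers will be absent from the baseline contact or will not answer a link in time, so they will have no baseline value. The result is some loss of precision, small if most forms arrive before randomisation. The sample size does not change.
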